#### *Collection of Pregnancy Information:*

- *If a participant is determined to be pregnant during the study (after receiving a dose of the study intervention), the investigator will report the pregnancy to the sponsor or delegate and collect follow-up information on the participant and the neonate. Generally, follow-up will not be required for longer than 6 weeks beyond the estimated delivery date. Any termination of pregnancy will be reported, regardless of fetal status (presence or absence of anomalies) or indication for the procedure.*

- *While pregnancy is not considered to be an AE or a SAE, any pregnancy complication or elective termination of a pregnancy will be reported as an AE or a SAE. Any abnormal pregnancy outcome that comes to the attention of the investigator (e.g., spontaneous abortion, fetal death, stillbirth, congenital anomalies, ectopic pregnancy) is considered to be a SAE.*
- *Any pregnancy-related SAE that occurs after study participation and is made known to the investigator and is assessed as related to the study intervention will be reported to the sponsor or the sponsor's designee. The investigator is not obligated to actively seek such information in former study participants who become pregnant during the study.*

#### **Contraception Guidance:**

~~Women physically capable of pregnancy must agree to use an acceptable method of avoiding pregnancy for one year after study intervention.~~

~~Acceptable methods of avoiding pregnancy include at least one of the following:~~

- ~~sexual abstinence (not engaging in sexual intercourse)~~
- ~~a confirmed sterile partner~~
- ~~use of at least 2 of the contraceptive methods shown below:~~
  - ~~o hormonal contraceptives (oral, injection, transdermal patch, or implant)~~
  - ~~o IUD~~
  - ~~o male or female condom~~
  - ~~o diaphragm.~~

~~Adequate contraception does not apply to participants of childbearing potential with same sex partners, when this is their preferred and usual lifestyle.~~

- i. ~~The investigator will collect follow up information on the participant and the neonate and the information will be forwarded to the sponsor. Generally, follow up will not be required for longer than 6 weeks beyond the estimated delivery date. Any termination of pregnancy will be reported, regardless of fetal status (presence or absence of anomalies) or indication for the procedure.~~
- j. ~~While pregnancy itself is not considered to be an AE or SAE, any pregnancy complication or elective termination of a pregnancy will be reported as an AE or SAE. Abnormal pregnancy outcomes (eg, spontaneous abortion, fetal death, stillbirth, congenital anomalies, ectopic pregnancy) are considered SAEs.~~
- ~~Any pregnancy related SAE that occurs after study participation and is made known to the investigator and is assessed as related to the study intervention will be reported to the sponsor or the sponsor's designee. The investigator is not obligated to actively seek this information in former study participants.~~

## Section 10.4 Appendix 4: Toxicity Tables

The following toxicity tables are extracted from the FDA Guidance *for* to the Industry

### Notes to Table 9:

\*\* “ULN” is the upper limit of the normal range.

GGT grading is not provided in the FDA toxicity grading scale tables. The following grading scale is from the U.S. Department of Health and Human Services, Common Terminology Criteria for Adverse Events, *Version 5.0* [US HSS 2017]:

Other:

eg changed to e.g.

ie changed to i.e.

added missing comma's where applicable

corrected minor spelling errors

updated table of content

updated first use of abbreviation as appropriate

changed subject to participant throughout

## Version 3.0, dated 10 December 2021

**Rationale for v3.0 (changes to v2, 20 July 2021):** The update from v2 to v3, was prepared to define the responsibilities of the Safety Review Team, the sponsor Chief Medical Officer, and the Independent Data Monitoring Committee.

Other minor changes were made for correction or clarification. All changes are provided below. New text is shown in bold italics and old text is shown with strikethroughs.

### Synopsis

**Safety Review Team:** A SRT will be established as the team responsible for *recommending dose escalation or dose expansion to the sponsor's Chief Medical Officer* ~~dose escalation decisions and proceeding to dose expansion.~~

~~Meetings of the SRT to provide a recommendation on dose escalation or dose expansion will occur during the Dose Escalation Phase when all participants in the currently dosed cohort have completed Day 15 to decide on proceeding to each subsequent dose escalation cohort will occur when all participants in the current cohort complete Day 15.~~

### Schedule of Activities, Table 2 continued.

A correction was made to the visit window for Day 3 Visit 3 in the table header on the second page of the table to align with the table header on the first page of the table. The window was corrected to  $\pm 0$  days.

V3
D3
$\pm 0$ d

### Section 8.1 Safety Assessments

Prior to opening ~~each of~~ Cohorts 2, 3 and 4 ~~and~~ 2 and 3 together, **Cohort 4, and Cohort 5, respectively**, to enrollment, the SRT will conduct a safety assessment of data for the previous cohort/s collected ~~for when~~ all participants *in the currently dosed cohort have completed Day 15.*, following the study intervention.

### Section 8.2.6 Safety Review Team

A SRT will be established as the team responsible for *recommending* dose escalation or ~~decisions and decision on proceeding to~~ dose expansion *to the sponsor's Chief Medical Officer.* *The SRT will operate according to the Safety Review Team Plan.*

~~Meetings of the SRT to provide a recommendation on dose escalation or dose expansion decide on proceeding to each subsequent cohort will occur during the Dose Escalation Phase when all participants in the currently dosed cohort have completed Day 15.~~

If a pausing event does not occur, dose escalation or moving to the Dose Expansion Phase cohort *will be recommended by the SRT* can occur.

If a pausing rule is met, the SRT will ask the IDMC to conduct a review of unblinded safety data. The IDMC will make a recommendation to the sponsor regarding the further conduct of the study (*See Section 8.2.7.*).

~~The SRT will consist of a panel of at least 4 members, including the Gates MRI clinical lead, the Gates MRI safety lead, the study Medical Monitor, and the site principal investigator. The SRT members are part of the study team and will review blinded safety data.~~

### Section 8.2.7 Independent Data Monitoring Committee

~~The role of the IDMC will be to (a)-review unblinded safety data if a pausing rule is met monitor the progress of the study, (b) review blinded safety data provided by the SRT, (c) review unblinded safety data if a pausing rule is met, and (d) make recommendations to the sponsor on further conduct of the study if a pausing rule is met.~~

Section 10.2.6 SAEs, AESIs, and Serious ADR Reporting

#### **Other Events Requiring Immediate Reporting**

~~The investigator must report the following events by scanning and emailing, or faxing the appropriate form to the sponsor or delegate within 24 hours of becoming aware of the event:~~

~~Withdrawal of consent during the study for medical reasons (Immediately Reportable Event Form)~~

~~Emergency unblinding (Immediately Reportable Event Form)~~

~~Protocol violation affecting the safety of a participant or involving the study intervention administration process (Immediately Reportable Event Form)~~

~~Any event that, in the opinion of the investigator, precludes further administration of the study intervention (Immediately Reportable Event Form, unless meets SAE criteria)~~

~~Pregnancy (Immediately Reportable Event Form, and Pregnancy Notification Form)~~

## Version 4.0, dated 21 January 2022

**Rationale for v4.0 (changes to v3, 10 December 2021):** After the study site provided information that a large proportion of screening failures has been due to inability to meet the body mass index (BMI) requirement, the sponsor agreed to raise the BMI eligibility inclusion criterion to reflect real world conditions, without affecting the safety of potential participants. The CDC criterion for obesity is a BMI>30; therefore, the updated inclusion criterion kept the BMI below this value. In addition, text was clarified for the exclusion criterion regarding timing of screening relative to a previous investigational drug.

The text regarding screening failures was modified after approximately 30% of screen failures in Cohort 1 did not meet the BMI eligibility requirement. Therefore, participants previously excluded due to BMI  $\geq 25$  kg/m^2 may be rescreened once, under this amendment. Participants who also initially failed screening for other reasons may also be rescreened once.

All changes are provided below. New text is shown in bold italics and old text is shown with strikethroughs.

### Section 5.1 Inclusion Criteria

#### Weight

3. Body mass index (BMI) 18 to ~~24.9~~ **29.9** kg/m^2 (inclusive)

### Section 5.2 Inclusion Criteria

#### Prior/Concurrent Clinical Study Experience

11. Participation in an interventional clinical trial and/or receipt of any investigational drug within ~~30 90~~ days *or 5 half-lives of the investigational drug before the first day of study drug dosing in this study, whichever is longer* prior to administration of study drug on Day 1.

### Section 5.4 Screen Failures

~~Rescreening assessments as outlined below may be performed after obtaining informed consent can be done at any time during the screening window (Day -30 to Day -2; SoA, Section 1.3), except for written informed consent, which must be completed prior to any rescreening procedure.~~

Rescreening is only permitted under one or more of the following *scenarios* conditions:

- If a participant presents with an acute illness on the day of planned study intervention, e.g., elevated temperature, acute respiratory or gastrointestinal illness, or urinary tract infection (UTI), and meets all other eligibility criteria and can be rescreened within the originally defined screening window (SoA, Section 1.3). *A new participant number is not required. If the participant is rescreened during the original screening window, obtaining a second informed consent of the participant is not required.*

- If there are technical difficulties with phlebotomy at screening (e.g., laboratory reports hemolyzed blood), technical error in running the laboratory tests or an abnormal urine analysis due to menstruation or UTI, and the participant can be rescreened within the originally defined screening window (SoA, Section 1.3). *A new participant number is not required. If the participant is rescreened during the original screening window, obtaining a second informed consent of the participant is not required.*
- If a participant is undergoing screening and the study reaches a pausing rule. The participant may **be rescreened** when and if the IDMC recommends, and the Sponsor determines, that the study may continue. *A new participant number is not required. If the participant is rescreened during the original screening window, obtaining a second informed consent of the participant is not required.*
- *If a participant fails to meet eligibility criteria upon initial screening, a one-time only rescreening for eligibility may be performed. In this case, the participant must receive a new participant number after signing a new informed consent.*

~~Repeat screening procedures may be performed as long as they are completed within the screening window.~~

Minor change: On title page version is represented by v instead of V for consistency with version history page and header.

Signature Page for Gates MRI-RSM01-101 Protocol Version 4.0 (21 Jan 2022) v7.0

e-Sig Approval	[REDACTED]
	Clinical Development 25-Jan-2022 19:39:18 GMT+0000

Head of Biometrics, Gates MRI

Date: _____

Clinical Development Leader, Gates MRI

List of Abbreviations

ADA	Anti-drug antibody
ADaM	Analysis data model
AE	Adverse event
AESI	Adverse event of special interest
AUC	Area under the (time) curve (e.g., capillary blood-concentration time curve)
BLQ	Below limit of quantification
C_{D91}	Day 91 capillary blood concentration of RSM01
C_{D151}	Day 151 capillary blood concentration of RSM01
C_{\max}	Maximum capillary blood concentration of RSM01
C_{\min}	Minimum capillary blood concentration of RSM01
CL	Total body clearance
CL/F	Apparent total body clearance
CSR	Clinical study report
ECG	Electrocardiogram
eCRF	Electronic case report form
EC90	90% maximal effective concentration
F	Bioavailability
Gates MRI	Bill & Melinda Gates Medical Research Institute
GGT	Gamma glutamyl transferase
HIV	Human immunodeficiency virus
ICH	International Council for Harmonization of Technical Requirements for Pharmaceuticals for Human Use
IDMC	Independent Data Monitoring Committee
IM	Intramuscular
IV	Intravenous
IXRS	Interactive voice/web response system
mAb	Monoclonal antibody
Mg	Milligram
mL	Milliliter
NA	Not applicable
NCA	Noncompartmental analysis
PD	Pharmacodynamics
PK	Pharmacokinetics
PP	Per protocol
RSM01	Monoclonal antibody targeting Respiratory Syncytial Virus
RSV	Respiratory Syncytial Virus
Rsq	R squared
SAE	Serious adverse event
SAP	Statistical analysis plan
SRT	Safety Review Team
$t_{1/2}$	Apparent terminal half-life
T_{\max}	Time to maximum capillary blood-concentration of RSM01

VAMS	Volumetric absorptive microsampling
Vz	Volume of distribution
Vz/F	Apparent volume of distribution
λ_z	Elimination rate constant

1. Introduction

The high and continued burden of Respiratory Syncytial Virus (RSV) infection, especially among infants and young children, underscores the need for safe and effective prevention against RSV disease that is affordable in low- and middle-income countries (LMICs).

This Phase 1 study will evaluate the safety, tolerability, and pharmacokinetics in adults of an RSV monoclonal antibody (mAb) candidate engineered to be highly neutralizing and long acting, and to determine an appropriate dose with acceptable safety profile in adults, prior to administration to infants in a future clinical study. Adult participants will receive either intravenous (IV) or intramuscular (IM) doses of RSM01, which will enable the assessment of the safety profiles together with estimation of the human bioavailability following IM injection, which is the intended route of administration in infants.

The purpose of this statistical analysis plan (SAP) is to define the planned analyses of the study data to address the study objectives. This SAP is written based on protocol Gates MRI-RSM01-101, Version 4.0, dated 21 Jan 2022.

2. Objectives and Endpoints

2.1 Primary Objectives and Endpoints

Primary objective	Endpoint description

• To characterize the safety and tolerability of a single dose of RSM01	
• Unsolicited adverse events (AEs) through Day 151• All serious adverse events (SAEs) and AE of special interest (AESIs) through Day 151• Solicited systemic AEs for 7 days after dose administration (applies to both IV and IM doses)• Solicited local AEs for injection site reactions for 7 days after dose administration (only applies to IM doses)

2.2 Secondary Objectives and Endpoints

Secondary objectives	Endpoint description

• To characterize safety laboratory parameters following RSM01 administration	
• Safety laboratory parameters through Day 151

• To characterize the pharmacokinetics (PK) following RSM01 administration	
PK parameters including:
 
• Area under the capillary blood-concentration time curve from zero to infinity ($AUC_{0-\infty}$)• Day 91 concentration and area under the capillary blood-concentration time curve (C_{D91} and AUC_{0-D91})• Day 151 concentration and area under the capillary blood-concentration time curve (C_{D151} and AUC_{0-D151})• Maximum capillary blood-concentration (C_{max} following IM administration and C_0 following IV administration)• Minimum concentration (C_{min})• Time to maximum capillary blood-concentration (T_{max}) and apparent terminal half-life ($t_{1/2}$)• Systemic clearance (CL for IV or CL/F for IM)• Volume of distribution of RSM01 (V_z for IV or V_z/F for IM) through Day 151

• To characterize the formation of anti-drug antibodies (ADAs) following RSM01 administration	
• Incidence of ADAs to RSM01 through Day 151

The dose expansion phase will have one cohort:

- Cohort 5: participants to receive RSM01 IM (n=24) at a dose to be determined (TBD mg IM) or placebo (n=4).

The tentatively determined dose to be evaluated in the Expansion Phase Cohort is ≥ 300 mg to ≤ 600 mg IM. Final selection of the dose administered to Cohort 5 will be made by the sponsor and informed by available RSM01 PK data from the Dose Escalation Phase.

Figure 1: Schema of Study Design and Dosing Procedures

Pausing rules (reasons for pausing the study) are in effect during the active enrollment and dosing period. Any one of the following will prompt a study pause:

- death in any participant in whom the event causing death is judged to be related to the study drug by the investigator.
- any occurrence in any participant of a SAE judged to be related by the investigator.
- any occurrence in any participant of an AESI (anaphylaxis, hypersensitivity reaction, and/or infusion reaction resulting in permanent discontinuation of study drug infusion during IV administration).
- any occurrence of Grade 3 or higher severity assessed to be related to the study drug by

the investigator.

- any occurrence of a clinically significant Grade 3 or higher laboratory abnormality assessed to be related to the study drug by the investigator.

If any of the pausing criteria are met, enrollment/patient accrual as well as dosing of enrolled participants will be suspended pending IDMC's review of all available safety data.

After screening, there will be a total of 11 visits over 151 days for the Dose Escalation Phase and a total of 5 visits over 151 days for the Dose Expansion Phase. An interim analysis will occur after all participants in the dose escalation cohorts (Cohorts 1 to 4) have reached Day 91. The primary analysis will occur after all participants in all 5 cohorts complete Day 151.

A more detailed Schedule of assessments can be found in [Section 15](#).

4. General Statistical Considerations

All statistical analyses will be conducted using statistical analysis system SAS® Version 9.4 or higher (SAS Institute, Cary, NC).

Descriptive statistics for continuous variables will include number of participants, mean, standard deviation (SD), median, minimum, and maximum, unless otherwise noted. For categorical variables, frequencies and percentages will be presented.

All tables, listings, and figures will be presented by cohort and treatment group. The treatment groups below will be used for presentations:

- RSM01 – 300 mg IV (Cohort 1)
- RSM01 – 300 mg IM (Cohort 2)
- RSM01 – 1000 mg IV (Cohort 3)
- RSM01 – 3000 mg IV (Cohort 4)
- RSM01 – TBD mg IM (Cohort 5)
- Total RSM01 treatment group
- Placebo IV (Cohorts 1, 3, 4)
- Placebo IM (Cohorts 2, 5)
- Total Placebo treatment group

All data listings will be sorted by cohort, treatment group, and participant number.

Study days are calculated with respect to study intervention administration date as below:

- If the assessment/observation date is on or after study intervention administration date, then Study Day = Assessment/Observation Date – Study Intervention Administration Date + 1.
- Otherwise, Study Day = Assessment/Observation Date – Study Intervention Administration Date.

Baseline will be defined as the last non-missing assessment (including repeated and unscheduled assessments) before study intervention administration, unless otherwise specified. If a patient

was rescreened, data from the rescreening period and not the original screening period will be used in the analyses as applicable.

For summary of safety assessments, if there are repeated measurements at a time point, the first non-missing assessment at that time point will be used in the summary tables.

For ADA-positive participants, the date of the first positive ADA result will be considered as the start date of ADA response.

Time to post-baseline ADA detection (weeks) will be calculated as:

$$\begin{aligned} & (\text{Date of first positive ADA assessment} - \text{Study Intervention Administration} \\ & \quad \text{Date} + 1) / 7 \end{aligned}$$

If the first positive ADA is prior to the start of treatment, the formula is revised to:

$$(\text{Date of first positive ADA assessment} - \text{Study Intervention Administration Date}) / 7$$

Duration of ADA immunogenicity response (weeks) is defined as:

$$(\text{Date of last positive ADA assessment} - \text{date of first positive ADA assessment} + 1) / 7$$

For participants with pre-existing positive, duration will be calculated from administration date of RSM01 rather than from date of first positive assessment.

The methodology and data handling specifications for PK data are detailed in [Section 8](#).

4.1. Handling of Missing Data

4.1.1 Missing or Partial Dates for Adverse Events

Missing or partial AE start dates will be imputed for the purpose of determining whether the AEs are treatment emergent. Data handling rules for missing or partial start/stop date for AEs are detailed in the table below. The missing or partial dates will be displayed in the data listings as reported on the electronic case report form (eCRF) rather than the imputed dates.

Date	Situation	Imputation Rule
AE Start Date	Only month and year are known, and month is prior to first dose date	Use the first day of the month
	Only month and year are known, and month is the same as first dose date	Use the first dose date
	Only month and year are known, and month is after first dose date	Use the first day of the month
	Only year is known, and year is after first dose date	Use Jan 1 of that year
AE End Date	Only month and year are known, and month is prior to last dose date	Use the last day of the month
	Only month and year are known, and month is the same as last dose date	Use the last dose date
	Only month and year are known, and	Use the first day of the month

	month is after last dose date	
	Only year is known, and year is before last dose date	Use Dec 31 of that year
	The estimated stop date is before a complete or imputed AE start date	Use the last day of the month of the AE start date

AE = adverse event
Note: Imputation of end date must be later than start date.

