4.1.2 Missing Incomplete Dates for Prior or Concomitant Medications

Missing or partial medication start or stop dates will be imputed for the purpose of determining whether the medication is taken concomitantly. Data handling rules for missing or partial start/stop date medications are detailed in the table below. The missing or partial dates will be displayed in the data listings as reported on the eCRF rather than the imputed dates.

Imputation rules for missing or partial dates (D=day, M=month, Y=year, T=time)			
Parameter	Missing	Additional conditions	Imputation Rule
Start date	D only	M and Y same as M and Y of first dose of study drug	Date of first dose of study drug
		M and/or Y not same as M and Y of first dose of study drug	First day of month
	M and D	Y same as Y of first dose of study drug	Date of first dose of study drug
		Y not same as Y of first dose of study drug	Use Jan 01 of Y
	M, D and Y	None--date completely missing	Date of first dose of study drug
	Stop date	M and Y same as M and Y of end of study	Date of end of study
		M and/or Y not same as M and Y of end of study	Last day of month
		Y same as Y of end of study	Date of last dose of study drug
		Y not same as Y of end of study	Use Dec 31 of Y
	M, D and Y	Medications that are not marked as ongoing - date completely missing	Date of end of study

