9.1 Adverse Events

9.1.1 Adverse Events Definitions and Reporting

An adverse event (AE) is defined as any untoward medical occurrence in a patient or clinical study participant, temporally associated with the use of study intervention, whether or not considered related to the study intervention.

A treatment-emergent AE (TEAE) is defined as any event not present before study intervention administration or any event already present that worsens in severity or frequency after study intervention administration.

A serious AE (SAE) is defined as any AE that results in any of the following outcomes: death, a life-threatening AE, inpatient hospitalization or prolongation of existing hospitalization, a persistent or significant incapacity or substantial disruption of the ability to conduct normal activities of daily living, or a congenital anomaly or birth defect. Important medical events that may not result in death, be life threatening, or require hospitalization may be considered serious when, based upon appropriate medical judgment, they may jeopardize the participant and may require medical or surgical intervention to prevent one of the outcomes listed in this definition.

An AE of special interest (AESI) is a preidentified and predefined event that has the potential to be causally associated with a study intervention that the sponsor will carefully monitor.

The AE's relationship to study treatment will be evaluated by the investigator or medically qualified designee (ie, investigator, study physician). The following relationships will be collected on eCRF: related, not related.

The severity of AEs will be classified by the investigator as mild, moderate, severe or potentially life threatening. An overall AE summary will be generated presenting the frequency and percentage of participants and the number of AEs for the following:

- Any TEAE
- Any treatment-related TEAE
- Any grade 1 TEAE
- Any grade 2 TEAE
- Any grade 3 or higher TEAE
- Any treatment-related grade 3 or higher TEAE
- Any SAE
- Any treatment-related SAE
- Any TEAE leading to dose interruption (IV route of administration)
- Any TEAE leading to study withdrawal
- Any death
- Any AESI

All AEs will be coded using MedDRA (version to be delineated in the CSR). The TEAEs will also be summarized by system organ class (SOC), preferred term (PT), by severity and relationship to study treatment.

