9.1.4 Unsolicited Treatment Emergent AEs, SAEs, and AESI

All unsolicited AEs, SAEs, and AESIs will be recorded from screening through Day 151.

Unsolicited AEs, SAEs, and AESIs will be coded according to MedDRA and summarized by System Organ Class (SOC), Preferred Term (PT) and highest severity. Clopper-Pearson exact 95% CIs will be calculated on the percentages of participants with AESIs. AEs leading to dose interruption for cohorts with IV route of administration and AEs leading to withdrawal from the study will also be summarized.

The number of events reported, the number of participants and percentage of participants who experience one or more unsolicited AE through Day 151, and one or more SAE, and one or more AESI from screening through Day 151 will be summarized by treatment group, as appropriate, and across all RSM01 dose levels and routes of administration, combined. The severity of each AE, and relationship between the AE and study intervention, will also be summarized.

For participants with more than 1 episode of the same event, the maximum severity will be used for tabulations. Participants reporting more than one occurrence for the PT term level being summarized will be counted only once.

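### The AE start-date rule has no stop-date exception, so an event recorded as ended before dosing can be flagged treatment-emergent

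*SAP*

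**What the plan says.** SAP 4.1.1 gives the purpose of the rule: "Missing or partial AE start dates will be imputed for the purpose of determining whether the AEs are treatment emergent". In its table, the row for the dosing month reads "Only month and year are known, and month is the same as first dose date", and the action is "Use the first dose date". The row does not mention the stop date. A start month before or after the dosing month goes to the first of that month. There is one year-only start row, for a year later than the dose.

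Only one row compares stop with start: "The estimated stop date is before a complete or imputed AE start date". It moves the stop to the end of the start month. The footnote adds "Note: Imputation of end date must be later than start date".

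SAP 9.1.1 sets the standard that the flag should meet: "A treatment-emergent AE (TEAE) is defined as any event not present before study intervention administration or any event already present that worsens". The worsening has to come after the dose. SAP 9.1.4 sets the collection window: "All unsolicited AEs, SAEs, and AESIs will be recorded from screening through Day 151".

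For medications, SAP 4.1.2 has a start row for "Y same as Y of first dose of study drug" when day and month are missing, and another for a date that is missing altogether. Both use the first dose date.

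**The concern.** Moving an unknown day in the dosing month to the dose date is a sensible conservative default while the event might have begun after dosing. It stops being sensible when the record itself shows that the event ended before the dose. The imputation rule and the TEAE definition then give opposite answers for the same record, and 4.1.1 is the section written to settle that question.

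At stake are the TEAE tables in SAP 9.1.1: the overall summary and the tables by system organ class, preferred term, severity and relationship. The escalation arms have 6 RSM01 participants each and the placebo groups have 3 (IV) and 5 (IM), so one misplaced event is visible. SAP section 13 says that statistical programming passed to a new provider, which is a further reason for the text to give one answer.

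**Working it through.** **The plan's own figure.** SAP 4.2 gives the AE rates at which at least one event is seen with 80% (90%) probability. With P = 1 − (1 − p)^n and n = 6:
- p = 0.2353: 1 − 0.7647^6 = 0.800
- p = 0.3187: 1 − 0.6813^6 = 0.900

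The figures for n = 24 and n = 48 reproduce as well. This point changes none of them. They do show that the plan is scaled on whether a group has one event or none.

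**The rule in general.** Let the dose fall on day d of a month and let the recorded stop be day s of the same month, with s < d. The start day is missing.
- As written, the imputed start is d. This is d − s days after the stop, for every such record, and it is on or after dosing.
- With a stop-date exception, the start is day 1. Since 1 ≤ s < d, it is never after the stop and always before the dose.

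**Example (assumed dates).** Dose 20 March, start recorded as March, complete stop 12 March.

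| | Imputed start | Treatment-emergent by date | Duration (stop − start + 1) |
|---|---|---|---|
| As written | 20 March | yes | 12 − 20 + 1 = −7 days |
| With exception | 1 March | no | 12 − 1 + 1 = 12 days |

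**Does another row repair it?** No. The stop-versus-start row covers an estimated stop, and the footnote covers an imputed end date. Both act on the stop and neither moves the start earlier. A complete stop date is left standing before the imputed start.

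**Effect of one record in a group with no other AE** (Clopper-Pearson 95%; for 0/n the upper limit is 1 − 0.025^(1/n), so 1 − 0.025^(1/6) = 45.9%):

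| Group | 0 events | 1 event |
|---|---|---|
| RSM01 escalation arm, 6 | 0% (0–45.9) | 16.7% (0.4–64.1) |
| RSM01 expansion arm, or pooled escalation, 24 | 0% (0–14.2) | 4.2% (0.1–21.1) |
| All RSM01, 48 | 0% (0–7.4) | 2.1% (0.1–11.1) |
| Placebo IV, 3 | 0% (0–70.8) | 33.3% (0.8–90.6) |
| Placebo IM, 5 | 0% (0–52.2) | 20.0% (0.5–71.6) |
| All placebo, 8 | 0% (0–36.9) | 12.5% (0.3–52.7) |

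Protocol 9.3.1 plans these intervals for unsolicited AEs. SAP 9.1.4 names them only for AESIs. Here they simply show scale.

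**Missing start rows.** Day 151 is dose date + 150 days, with a window of +7. A dose on 27 July gives 27 July + 150 = 24 December, and + 7 = 31 December. For anyone dosed by about 27 July, the whole post-dose period therefore lies in the dosing year, and the only year-only start row cannot apply to an in-study post-dose AE. A wholly missing start date has no row for anyone.

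**The case against.** The strongest reply is that such records should not be in the AE data. Protocol 8.2.1 directs conditions arising between consent and dosing to the medical history form, and Protocol 8.1.2 says the same of all pre-dose conditions. Both documents define an AE by its temporal association with study intervention, which an event that ended before dosing lacks. The SAP row for start months before dosing is weak evidence of intent: the table also speaks of a last dose in a single-dose trial, so it may be template wording.

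This makes the records uncertain and rare, but it does not exclude them. The table in Protocol 8.2.1 collects unsolicited AEs from screening. So do Protocol 8.2, Protocol 9.3.1 and SAP 9.1.4, and both schedules of activities mark AE recording at screening and Day −1.

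The second reply is that the 9.1.1 definition already excludes the event, so a careful programmer would not flag it. That is true of the definition. But the programmer would have to set aside an explicit rule whose stated purpose is to decide treatment-emergent status. The outcome depends on which section is followed, so the wording is *can be flagged*, not *will be*.

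The same reply limits the missing-row point. The SAP does not say that an event without an imputed start is left out of the TEAE tables. It gives no date rule for it.

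**Conclusion.** The gap is real and narrow. As written, the dosing-month row gives an impossible date order and a flag that contradicts the TEAE definition whenever five conditions meet: the event is on the AE page, its start day is missing, its start month is the dosing month, its stop date is complete, and that stop is before dosing. The documents give no rate for this combination, so the number of affected records cannot be derived. It is probably very small and may be zero. One record adds 16.7 percentage points to an otherwise empty arm of 6. The trial is descriptive, so no hypothesis test is affected.

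A reader might infer more than the documents support:
- **That TEAE counts are the primary endpoint.** The endpoint is worded as unsolicited AEs through Day 151, with SAEs, AESIs and solicited AEs. The treatment-emergent restriction comes from the 9.1.1 tables and the 9.1.4 heading. SAEs and AESIs are counted from screening, so this imputation does not change those counts.
- **That the last end-date row would stretch the event to month end, as a long post-dose reaction.** That row covers estimated stop dates, not complete ones.
- **That a false dosing-day onset would appear in the results.** Onset summaries are specified for solicited AEs only, and listings show dates as reported.
- **That about half of screening-period events are affected.** For a 30-day month, 14.5 of 30 screening days (48%) fall on average in the dosing month. That is a share of days. It includes events with unknown or post-dose stops, for which the default is right.
- **That the year-only row is unusable for doses up to 3 August.** That cutoff ignores the +7-day window; about 27 July is correct.

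**What to change.** In SAP 4.1.1, change the action in the dosing-month start row to: *Use the first dose date, unless a complete recorded stop date is before the first dose date, in which case use the first day of the month and do not classify the event as treatment-emergent.* A complete stop date is the right condition here, because a stop known only to the dosing month does not show that the event ended before the dose.

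Add a start row for a year-only date in the dosing year and for a wholly missing date: *Use the first dose date unless the recorded stop (complete date, or month and year) is before dosing.* This takes the dose-date default of SAP 4.1.2 and adds a stop-date exception that 4.1.2 does not have.

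The cost is a few words of SAP text, one added row and a matching condition in the AE dataset program. No new data and no protocol amendment are needed. Events with an unknown stop, or a stop on or after dosing, keep the conservative classification. The change is best made before any unblinded review.
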